4.2 TREATMENT PERIOD

Subjects who meet all eligibility criteria, as per data gathered from Screening Period are to be treated. All subjects who fail to meet eligibility criteria will be considered screen failure and exit the study without further evaluation

The maximum sample size for this study is 90 subjects that will be followed by treatment according to the schedule described above.

In Part 1 of the study, eligible subjects will be randomized to 1:1 to one of the two study arms to receive Leronlimab (PRO 140) 700 mg (Group A), or placebo (Group B) as two subcutaneous injections, given once per week (\pm 1 day) for up to 13 weeks during the treatment period.

- PRO 140 700mg SC weekly injection (Group A)
- Placebo 0 mg SC weekly injection (Group B)

The study treatment (PRO 140 700 mg or placebo SC injections) will be administered by a licensed healthcare professional once a week at the study site.

In Part 2 of the study, eligible subjects will be enrolled to receive leronlimab (PRO 140) 350 mg as one injection, given once per week (\pm 1 day) for up to 13 weeks during the treatment period.

- PRO 140 350mg SC weekly injection

The study treatment (PRO 140 350 mg SC injection) will be administered by a licensed healthcare professional once a week at the study site.

Treatment Visit 1 (T1)

The following assessments will be performed at the first treatment visit, unless otherwise specified:

Pre-Treatment

- Confirmation of eligibility criteria by reviewing test results and other criteria assessments performed at Screening Visit (see [Section 7.2](#))
- Vital Signs and body weight measurement (see [Section 7.6](#)),
- Physical examination (see [section 7.7](#)),
- 12-lead Electrocardiogram (see [Section 7.8](#))
- Change in concomitant medications (see [Section 7.5](#)),
- Any changes in medical history since Screening Visit (see [Section 7.4](#)),
- Randomization only applicable for Part 1 of the study (see [Section 8.4](#))
- Collection of lab specimens (see [Section 7.9](#)) for
 - Complete blood count
 - Biochemistry
 - Urine pregnancy test, for female subjects of childbearing potential
 - Urine sample for urinalysis parameters
 - FibroTest
 - Anti-Drug Antibodies (ADA) to PRO 140
 - PK evaluations
 - Serum pro-inflammatory cytokine/chemokine evaluations
 - Monocyte/T cell CCR5 biomarker assay

Administration of study treatment /PRO 140 or placebo/

PRO 140 or placebo is administered as subcutaneous injection in the abdomen weekly. In part 1 of the study, a total of 700 mg (175 mg/mL) or placebo is delivered as two injections of 2 mL on opposite sides of the abdomen. In Part 2 of the study, a dose of 350 mg of leronlimab (PRO 140) (175 mg/mL) will be delivered as one injection of 2 mL and administered subcutaneously in the abdomen.

Note: All study treatments (PRO 140 or placebo) must be administered by a licensed healthcare professional.

Post-Treatment

- Injection Site Reaction Assessment (see [Section 7.11](#))
- Assessment of Adverse Events (AE) (see [Section 9.1](#))
- Vital Signs (see [Section 7.6](#)) will be assessed within 15 minutes of study treatment administration.

After treatment administration, subjects who meet any criteria for discontinuation of study treatment as specified in [Section 5.1](#) of the protocol, will undergo End of Treatment (EOT) Visit assessments and enter the Follow-up Phase of the study.

Treatment Visit 2 (T2) to Treatment Visit 13 (T13)

The following assessments will be performed at each visit, unless otherwise specified:

- Assess for any AEs (see [Section 9.1](#))
- Concomitant medications assessment (see [Section 7.5](#))
- Vital Signs and body weight measurement (see [Section 7.6](#)) (weight only on visits T2, T6, T10)
- Symptom-directed physical examination at clinic visits (see [Section 7.7](#)) (only on visits T2, T6, T10)
- 12-lead Electrocardiogram (see [Section 7.8](#)) (only on visits T2, T6, T10)
- Collection of lab specimens at T2 , T6, T10 (see [Section 7.9](#)) for:
 - Complete blood count
 - Biochemistry
 - Urine sample for urinalysis parameters
 - Urine pregnancy test, for female subjects of childbearing potential (T6 and T10 only)
 - FibroTest
 - Anti-Drug Antibodies (ADA) to PRO 140
 - PK assessment
 - Serum pro-inflammatory cytokine/chemokine evaluations
 - Monocyte/T cell CCR5 biomarker assay

- Leronlimab (PRO 140) Administration (see [Section 6.4](#))
- Injection Site Reaction Assessment (see [Section 7.11](#))
- Subject-perceived Injection Site Pain Assessment (see [Section 7.12](#))

Note: Subject-perceived injection site pain will be assessed using 11-point Numeric Pain Rating Scale from 0 to 10 prior to study treatment administration assessing average pain at injection site since last treatment. “0” meaning “no pain” and “10” meaning “worst possible pain”.

End of Treatment (EOT) Visit

Subjects who complete the treatment period will undergo End of Treatment (EOT) Visit. The following assessments will be performed for the subjects:

- Assess for any Adverse Events (see [Section 9.1](#))
- Changes in Concomitant medications (see [Section 7.5](#)),
- Physical examination (see [Section 7.7](#)),
- Vital Signs and body weight measurement (see [Section 7.6](#)),
- Subject-perceived Injection Site Pain Assessment (see [Section 7.12](#)),
- 12-lead Electrocardiogram (see [section 7.8](#)),
- Liver MRI (see section [7.14](#))
- Collection of Blood Specimens (see [section 0](#)) for:
 - Complete Blood Count
 - Biochemistry
 - FibroTest
 - Anti-Drug Antibodies (ADA) to PRO 140
 - PK assessment
 - Serum pro-inflammatory cytokine/chemokine evaluations
 - Monocyte/T cell CCR5 biomarker assay

Note: In case subjects have already completed their EOT/ET and FU visits, site should use the Unscheduled Visit option to collect blood sample for Monocyte/T Cell CCR5 analysis.

- Urine pregnancy test, for female subjects of childbearing potential.
- Urine sample for urinalysis parameters

Early Termination (ET) Visit

Subjects who meet any criteria for discontinuation of study treatment as specified in [Section 5.1](#) of the protocol, will undergo Early Termination (ET) Visit.

The following assessments will be performed:

- Assess for any Adverse Events (see [Section 9.1](#))
- Changes in Concomitant medications (see [Section 7.5](#)),
- Symptom-directed physical examination (see [Section 7.7](#)),
- Vital Signs and body weight measurement (see [Section 7.6](#)),
- 12-lead Electrocardiogram (see [section 7.8](#)),
- Liver MRI (see section [7.14](#))
- Collection of Blood Specimens (see [section 0](#)) for:
 - Complete Blood Count
 - Biochemistry
 - FibroTest
 - Anti-Drug Antibodies (ADA) to PRO 140
 - PK assessment
 - Serum pro-inflammatory cytokine/chemokine evaluations
 - Monocyte/T cell CCR5 biomarker assay
- Urine pregnancy test, for female subjects of childbearing potential.
- Urine sample for urinalysis parameters

4.3 FOLLOW-UP PERIOD

Follow-up visit will be conducted 28 (\pm 3) days after the End of Treatment (EOT) or Early Termination (ET) Visit. All subjects will be followed for biochemistry lab assessment, anti-drug antibodies (ADA) to PRO 140, PK assessment, serum pro-inflammatory assessment, blood sample for Monocyte/T cell CCR5 biomarker assay vital signs, symptom-directed physical exam, adverse events, and concomitant medications assessment.

Subjects who discontinue treatment for unacceptable adverse event(s) will be followed until resolution or stabilization of the adverse event (i.e. the grade is not changing).

4.4 UNSCHEDULED VISITS

In the event that the subject will return to clinic at a time other than a regularly scheduled study visit, the visit will be regarded as an unscheduled visit. Assessments at unscheduled visits are at the discretion of the Investigator. All pertinent findings, including adverse events or changes in medications, will be noted in the eCRF.

Any hospitalization or ER visits in between the scheduled visits should be promptly notified to the site staff.

5 SUBJECT COMPLETION, WITHDRAWAL AND CRITERIA FOR STOPPING THE STUDY

A subject who has completed the 14-week treatment period and 4-week follow-up period will be considered as having completed the study.

5.1 SUBJECT WITHDRAWAL

A subject who enters the Treatment Phase but does not complete the study, as defined in this section, is considered to have prematurely withdrawn (early terminated) from the Study.

All subjects have the right to withdraw at any point during treatment without prejudice to future care. It will be documented whether or not each subject completed the clinical study. If for any subject, study treatment or observations were discontinued, the reason(s) will be recorded.

Subjects WILL be withdrawn from the study, in consultation with the Medical Monitor and the Investigator, if any of the following are met:

- A subject is significantly non-compliant with the requirements of the protocol.
- The Investigator determines that it is in the best interest of the subject.
- Subject chooses to withdraw or is withdrawn due to an adverse event
- A subject becomes pregnant

Note: The pregnancy will be followed to term for safety follow-up. Relevant safety information collected after the study has completed will be reported as supplemental information.

- Discontinuation of study by Sponsor
- Subject becomes lost to follow-up (LTf)
- Subject experiences unacceptable toxicity
- Subject voluntarily withdraws from treatment (follow-up permitted)
- Subject withdraws consent (no follow-up permitted)

Discontinuation of study treatment for the individual subject MAY occur if, in consultation with the Medical Monitor and the Investigator, any of the following are met:

- A subject is treated with a prohibited medication.
- Diabetic subjects with an increased HbA1c results of >9% or experiencing significant changes in glucose control requiring modification to the dosage or regimen of antidiabetic medication
- Major protocol violation ([Section 0](#))

- Subjects who have two occurrences of a Grade 2 or higher allergic/hypersensitivity reaction directly related to the study drug that lead to permanent discontinuation of study drug.
- Subjects experiencing grade 3 or higher AE (per CTCAE v5.0) that is possibly or probably related to the study drug OR grade 4 or higher AE regardless of attribution to the study drug.
- Subjects considered to potentially have Drug-Induced Liver Injury (DILI) as described below.

Drug- induced liver Injury (DILI)

If subjects with abnormal baseline liver indices develop elevations of AST or ALT $>2x$ baseline or Total Bilirubin (TBL) $>1.5x$ baseline values during the study, the tests will be repeated within 48-72 hours. If there are persistent elevations (AST or ALT $>2x$ baseline or TBL >1.5 baseline values) upon repeat testing, then close observation of the subjects per below should be implemented and discontinuation of the study treatment will be considered as per [Section 5.1](#). During the close observation period, liver enzyme and serum bilirubin tests will need to be repeated two or three times weekly. Frequency of retesting can decrease to once a week or less if abnormalities stabilize or the study treatment has been discontinued and the subject is asymptomatic.

Additionally, further gastroenterology or hepatology consultations and/or liver biopsy can be considered per Investigator's discretion.

If patient is unable to come to clinic for blood draw during the close observation period, laboratory testing can be performed locally, and the results should be promptly communicated to the investigator site. A decision to discontinue or temporarily interrupt the study drug will be considered based on factors that include how much higher than baseline the ALT and AST are relative to the upper limit of normal (ULN) and how much the AST and ALT levels have increased relative to baseline, in addition to whether there is a concomitant elevation of bilirubin or INR. The study treatment will be discontinued or temporarily interrupted under the following conditions:

- If Baseline Measurements (BLM) were $<2x$ ULN, The study treatment should be discontinued if ALT or AST increases to $>5x$ BLM
- If BLM was $2x$ ULN but $<5x$ ULN, The study treatment will be discontinued if ALT or AST increases to $3x$ BLM
- If BLM was $5x$ ULN, The study treatment will be discontinued if ALT or AST increases to $>2x$ BLM
- If ALT or AST increases $>2x$ BLM and the increase is accompanied by a concomitant increase in TB to $>2x$ BLM or the INR concomitantly increases by 0.2, The study treatment will be discontinued

- If any subject presents with signs or symptoms of fatigue, nausea, vomiting, right upper quadrant pain or tenderness, fever, rash, and or eosinophilia (>5%), the study treatment should be discontinued

Note: For the purpose of the assessment of drug-induced liver injury (DILI), Baseline Measurements (BLM) for lab values (such as AST, ALT, total Bilirubin) refers to the average (mean) value of Screening Visit (SV) and T1 Visit. If liver function tests are repeated during Screening Phase, the average (mean) value of all Screening Visit tests and T1 Visit will be used to calculate the Baseline Measurements.

All data normally collected at the scheduled EOT Visit should be recorded at the time of premature discontinuation.

If a subject fails to return for the scheduled study visit or is discontinued from the study, an attempt will be made to determine the reason(s). If the subject is unreachable by telephone, a registered letter will be sent to the subject requesting that he/she contact the clinic.

All patients with an ongoing SAE at the Post-Study (Follow-up) Visit (scheduled or premature) must be followed until the event is resolved (with or without sequelae) or deemed stable.

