3.3 ELIGIBILITY CRITERIA

Inclusion Criteria

Subjects are required to meet ALL of the following criteria for enrollment into the study:

1. Subject is a male or female between 18 to 75 years of age inclusive.
2. Evidence of nonalcoholic steatohepatitis (NASH) based on one of the following criteria:
 - Criteria 1: Histologically-confirmed diagnosis of NASH on a liver biopsy, or
 - Criteria 2: FibroScan or Shearwave US during screening (or within 6 months before screening) shows kPa ≥ 7 but < 14 and CAP ≥ 260 .
3. Subject shows presence of hepatic fat fraction as defined by $\geq 8\%$ on MRI-PDFF and cT1 ≥ 800 ms at Screening.
4. Has had a stable body weight ($\pm 5\%$) within 6 months prior to Screening.
5. Body Mass Index (BMI) ≥ 28 kg/m² at Screening
6. Has clinically normal resting 12-lead ECG at Screening Visit or, if abnormal, considered not clinically significant by the Principal Investigator.
7. Laboratory Screening results as indicated below:
 - a. AST:ALT Ratio ≤ 1 , if AST or ALT value is $>$ ULN
 - b. Screening Liver enzymes (AST, ALT, and ALK PHOS) $< 5 \times$ ULN.
 - c. Total Bilirubin ≤ 1.3 mg/dL (except if Gilbert's Disease)
 - d. Platelet count $\geq 150,000/\text{mm}^3$
 - e. International normalized ratio (INR) < 1.3
 - f. Estimated Glomerular Filtration Rate (eGFR) $\geq 60/\text{mL/min}$
 - g. Glycosylated hemoglobin (HbA1c) $< 9\%$.
 - h. TSH within normal reference range.

Note: Any subject with a non-clinically significant TSH value outside of the normal range may be enrolled if their T3 and free T4 values are within the normal range.

8. Subjects with pre-diabetes or type 2 diabetes will be allowed to participate if the following criteria is met:
 - Subjects who are taking anti-diabetic medications should be on a stable dose for a period of at least 3 months prior to Screening and do not anticipate clinically significant dose adjustments during the course of study.

- Subjects must be on a stable diet/lifestyle regimen for at least 3 months prior to screening and do not anticipate a clinically significant change during the course of study.
- 9. Subjects who are taking Vitamin E should be on a stable dose of Vitamin E (if \geq 400 IU) for a period of at least 4 weeks prior to Screening and do not anticipate dose adjustments for the duration of the study.

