7.9 CLINICAL LABORATORY ASSESSMENTS

Blood samples will be collected for analysis of the following parameters:

- Hematology (Complete Blood Count) will be performed at SV, T1 (prior to first dose), T2, T6, T10, EOT/ET visits.
- Biochemistry will be performed at SV, T1 (prior to first dose), T2, T6, T10, EOT/ET and FU visits.

Note: Screening laboratory test can be repeated once during the 28-day screening window based on the Investigator's clinical judgement).

- Serum pro-inflammatory biomarkers including IL-1 alpha, IL-1 beta, IL-6, RANTES (CCL5), TNF-alpha, TNF-beta, CRP will be performed at T1 (prior to first dose), T2 (pre-dose), T6 (pre-dose), T10 (pre-dose), EOT/ET and FU visits.
- FibroTest (requires fasting for 12 hours or more) combines 5 standard biomarkers (gamma-glutamyltransferase, total bilirubin, alpha-2-macroglobulin, apolipoprotein A1, and haptoglobin). The Acti-Test adds a marker for inflammatory activity (alanine aminotransferase: ALT). FibroTest will be performed at SV, T1 (prior to first dose), T2, T6, T10, EOT/ET visits.
- Serology tests including HBs Ag, HCV Ab and HCV RNA (only performed if HCV Ab is positive), HIV Ab, Hepatitis A and Hepatitis E Abs will be performed at SV.
- Anti-Drug antibodies (ADA) to PRO 140 at T1 (prior to first dose), T2 (pre-dose), T6 (pre-dose), T10 (pre-dose), EOT/ET and FU visits.
- PK assessment at T1 (prior to first dose), T2 (pre-dose), T6 (pre-dose), T10 (pre-dose), EOT/ET and FU visits.

- Serum pregnancy test (for female subjects of childbearing potential) at SV.
- Monocyte/T cell CCR5 biomarker assay at T1 (prior to first dose), T2 (pre-dose), T6 (pre-dose), T10 (pre-dose), EOT/ET and FU visits.

Note: In case subjects have already completed their EOT/ET and FU visits, site should use the Unscheduled Visit option to collect blood sample for Monocyte/T Cell CCR5 analysis.

Urine samples will be collected for analysis of the following parameters:

- Urine pregnancy at T1 (prior to first dose), T6, T10, EOT/ET visits.

Note: A urine sample will be collected from female subjects of childbearing potential. This test will be performed at the study site using a commercially available kit.

- Urine analysis testing at SV, T1 (prior to first dose), T2, T6, T10, EOT/ET visits.

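### Protocol 5.1 mandates the 48-72 h liver retest only for subjects with abnormal baseline liver tests, and its last DILI condition names symptoms without any liver-test condition

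*Protocol*

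**What the plan says.** The DILI text in Protocol 5.1 has two steps.

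- **Retest and close observation.** The step opens "If subjects with abnormal baseline liver indices develop elevations of AST or ALT" above twice baseline, or total bilirubin above 1.5 times baseline. The tests are then repeated within 48-72 hours. If the rise persists, "During the close observation period, liver enzyme and serum bilirubin tests will need to be repeated two or three times weekly", less often once values stabilise, or once drug is stopped and the subject has no symptoms. The section does not define an abnormal baseline.
- **Five stopping conditions.** Their lead-in is "The study treatment will be discontinued or temporarily interrupted under the following conditions". Three are ALT/AST multiples of the baseline measurement (BLM, the mean of the screening and T1 values). For BLM below 2 times ULN, the stop is ALT or AST above 5 times BLM. The fourth needs ALT or AST above 2 times BLM "and the increase is accompanied by a concomitant increase in TB to" more than 2 times BLM, or an INR rise of 0.2. The fifth begins "If any subject presents with signs or symptoms of fatigue, nausea, vomiting, right upper quadrant pain or tenderness, fever, rash" and goes on to eosinophilia above 5%. It names no liver test.

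On eligibility (Protocol 3.3), criterion 7a limits the AST:ALT ratio only "if AST or ALT value is" above ULN. Criterion 7b, "Screening Liver enzymes (AST, ALT, and ALK PHOS"), sets only an upper limit of 5 times ULN. Neither requires a raised enzyme.

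On timing, Protocol 7.9 says: "Biochemistry will be performed at SV, T1 (prior to first dose), T2, T6, T10, EOT/ET and FU visits".

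**The concern.** A subject who enters with normal liver tests and then shows a clear enzyme rise is the case in which a drug effect is easiest to suspect, because there is no raised baseline to explain it. Yet the mandated retest passes over this subject and covers one whose baseline was slightly raised. The larger relative rise can receive less required monitoring.

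The symptom condition has the opposite problem. The other four conditions each name an ALT or AST threshold; this one names none and applies to any subject. On its literal wording, a site would stop or interrupt drug for fatigue or a rash whatever the liver tests show. Nothing in the protocol tells the site to draw liver tests when such a symptom appears.

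What is at stake is subject safety and consistent conduct across up to 20 centers.

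**Working it through.** The plan states no figure to reproduce. The check is a literal reading of the rules plus threshold arithmetic.

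**Inputs.** Reference ranges (Protocol 7.9): ALT 17-63 IU/L in men and 14-54 in women, AST 15-41, total bilirubin 0.2-0.9 mg/dL. Retest trigger 2 × BLM, stop 5 × BLM for BLM below 2 × ULN (Protocol 5.1). Biochemistry on days 1, 8, 36, 64 and 92 (Protocol Table 4-2).

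**1. What covers a subject with normal baseline AST, ALT and bilirubin.** The 5 × BLM stop and the combined stop apply. Below them, Protocol 7.9 requires investigator review of laboratory reports and leaves any repeat to judgement. Protocol 4.4 leaves the content of unscheduled visits to the investigator. Protocol 9.2 follows adverse events but sets no test interval. The weekly AE check in Protocol 4.2 would not detect a symptom-free rise. SAP 9.3.3 only lists, summarises and flags laboratory values. None of these mandates a retest.

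**2. The uncovered band for an isolated ALT or AST rise (above 2 × BLM, up to 5 × BLM), set against the trigger proposed under the fix.**

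| Test | Band at lowest normal BLM | Band at highest normal BLM | Proposed trigger, max(2 × BLM, ULN) | Stop, 5 × BLM |
|---|---|---|---|---|
| ALT, men | 34-85 | 126-315 | 63-126 | 85-315 |
| ALT, women | 28-70 | 108-270 | 54-108 | 70-270 |
| AST | 30-75 | 82-205 | 41-82 | 75-205 |

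At the highest normal BLM the band is 2.0 to 5.0 times ULN. At the lowest, part of it lies inside the normal range (34/63 = 0.54 times ULN for men), so deleting the word abnormal would not be enough: the trigger also needs a floor at ULN.

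**3. ALT example**, with normal baseline AST and bilirubin, and bilirubin and INR unchanged on treatment. BLM 60 rising to 250: 250/60 = 4.2 times BLM and 250/63 = 4.0 times ULN. The stop is 5 × 60 = 300, so neither a stop nor a retest is mandated. Compare BLM 70 (70/63 = 1.1 times ULN) rising to 250: 250/70 = 3.6 times BLM, below his stop of 5 × 70 = 350, but a retest within 48-72 hours is required.

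**4. Time to the next required test.** 36 − 8 = 64 − 36 = 92 − 64 = 28 days. A rise in the T2 sample could therefore wait nominally 28 days, with doses T3, T4 and T5 in between. If the comparison subject's rise persists, he has 25 to 26 days of close observation left: 25/7 × 2 = 7.1 to 26/7 × 3 = 11.1, or about 7 to 11 tests unless values stabilise.

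**5. Bilirubin example**, all baselines normal. 0.8 rising to 2.0 mg/dL: 2.0/0.8 = 2.5 times BLM and 2.0/0.9 = 2.2 times ULN. With ALT and AST at or below 2 × BLM there is no mandated retest. There is no numeric stop either, because the only bilirubin stop also needs an ALT or AST rise.

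**6. Does the proposed trigger always precede the stop?** max(2 × BLM, ULN) < 5 × BLM holds when BLM > ULN/5, that is above 63/5 = 12.6 (ALT, men), 54/5 = 10.8 (ALT, women) and 41/5 = 8.2 (AST). Every baseline inside the reference ranges qualifies. One below the lower reference limit may not.

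**7. Symptom condition.** T2 to T13 are 12 visits; T2, T6 and T10 have biochemistry, so 12 − 3 = 9 have no scheduled liver test. A symptom reported at one of those has no same-day result to set beside it.

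**The case against.** **On the retest.** A reader might infer that subjects with normal baselines have no liver-safety rule at all. The documents do not support that: two numeric stops apply. In addition, Protocol 5.1 lists grade 3 or higher AEs possibly or probably related to drug, and any grade 4 or higher AE, as grounds on which treatment may be stopped, and it withdraws subjects for unacceptable toxicity. An investigator who reviews every report is also unlikely to leave an ALT of 4 times ULN unrepeated for 28 days. All of that narrows the practical gap, but none of it sets a retest or an interval. Because an abnormal baseline is undefined, a site could count some other liver index and so bring a subject in. The examples therefore hold only where no index that the site counts was abnormal, and the lack of a definition is itself something to clarify.

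**On the symptom condition.** The DILI text elaborates one item, subjects considered potentially to have DILI. It sits in a list under a heading that makes discontinuation permissive and subject to consultation with the Medical Monitor and the Investigator. The sentences before the five conditions refer the decision to enzymes, bilirubin and INR. The condition was probably meant for suspected liver injury. This stands: mandatory stopping for symptoms alone is the strictest reading, not the only one. The lead-in and the phrase covering any subject still pull the other way, so the text is ambiguous.

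A reader might also infer that the condition would fire often, since Protocol 1.5 lists fatigue among the most common events in study 1302. That study gave single intravenous doses to 39 subjects with early HIV infection. In the subcutaneous study 2101 the most common events were diarrhea, headache, lymphadenopathy and hypertension, none of them on the list. Protocol 1.6 reports mainly mild injection-site reactions at 525 and 700 mg. The documents give no symptom rate for NASH patients.

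**Conclusion.** The main point holds on the wording. For a subject whose baseline AST, ALT and bilirubin are all normal, Protocol 5.1 mandates no retest after an isolated ALT or AST rise of more than 2 and up to 5 times BLM (as high as 5.0 times ULN), or after an isolated bilirubin rise. The next required test may be 28 days away instead of 48-72 hours. This rests on the literal text, on taking abnormal to mean outside the protocol's reference ranges, and on the investigator not choosing to test sooner.

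The symptom condition is a secondary point: an ambiguity that on its literal wording stops or interrupts drug without a liver-test condition. How often it would apply, and how many subjects fall into either case, cannot be derived from the documents.

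A reader might go on to infer damage to the primary analysis through extra early terminations. With no rate to work from, that is not shown and is not claimed. This is a safety-wording correction that should be made because it is specific and cheap.

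**What to change.** **Retest.** Apply the 48-72 hour repeat, and close observation if the rise persists, to all subjects. For normal baselines, trigger at ALT or AST above 2 × BLM and above ULN, or total bilirubin above 1.5 × BLM and above ULN. The sponsor's medical team should set the final thresholds and decide how to treat baselines below the lower reference limit. Cost: a short clarification and a few extra liver tests.

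**Symptom condition.** Require liver tests promptly when a listed symptom or eosinophilia occurs without a current result. Tie the stop or interruption to such a finding together with either ALT or AST above 2 × BLM, or total bilirubin above 1.5 × BLM and above ULN, without waiting for a confirmatory repeat. The bilirubin alternative is needed: with an ALT or AST condition alone, a symptomatic subject with an isolated bilirubin rise would lose the only DILI stop that now applies. Cost: symptomatic subjects with no rise in ALT, AST or bilirubin stay on treatment unless another rule in Protocol 5.1 applies.
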